6.5 Packaging and Labeling

BMS will provide ipilimumab at no cost for this study. Ipilimumab will be provided in open-label containers. The labels will contain the protocol prefix, batch number, content, storage conditions, and dispensing instructions along with the Investigational New Drug (IND) caution statement. Ipilimumab will be supplied at a concentration of 5 mg/mL in vials containing 10 ml or 40 mL solution.

6.6 Storage, Handling, and Dispensing

6.6.1 Storage

Ipilimumab must be stored in a secure area according to local regulations. The investigator must ensure that it is stored in accordance with the environmental conditions as determined by BMS and defined in the Investigator Brochure or SmPC/reference label. Ipilimumab must be stored at a temperature $\geq 2^{\circ}$ C and $\leq 8^{\circ}$ C.

6.6.2 Handling and Disposal

As with all injectable drugs, care should be taken when handling and preparing ipilimumab. Whenever possible, ipilimumab should be prepared in a laminar flow hood or safety cabinet using standard precautions for the safe handling of intravenous agents applying aseptic technique. Latex gloves are required. If ipilimumab concentrate or solution comes in contact with skin or mucosa, immediately and thoroughly wash with soap and water. After final drug reconciliation, unused ipilimumab solution should be disposed at the site following procedures for the disposal of anticancer drugs.

6.6.3 Dispensing

It is the responsibility of the investigator to ensure that ipilimumab is only dispensed to study subjects. The ipilimumab must be dispensed only from official study sites by authorized personnel according to local regulations.

6.7 Drug Ordering and Accountability

6.7.1 Initial Orders

Following submission and approval of the required regulatory documents, a supply of ipilimumab may be ordered from BMS. Investigators must complete a Drug Request Form and email it to [contact] and [contact]. Please fax to [contact] (U.S.) if you cannot send the form electronically.

Ipilimumab vials (10 mL and 40 mL) are shipped in quantities of ten. Allow 5 business days for shipment of drug from BMS receipt of the ipilimumab Clinical Supply Shipment Request form. Drug is protocol specific, but not patient specific.

All product will be shipped via Federal Express in a temperature-controlled container. Shipments will be made from BMS on Monday through Thursday for delivery onsite Tuesday through Friday. There will be no weekend or holiday delivery of drugs. It is possible that sites may have more than one ipilimumab clinical study ongoing at the same time. It is imperative that only product designated for this protocol number be used for this study. To help segregate product for this study from other investigational or marketed product, stickers bearing the BMS protocol number will be provided and should be affixed to the front of the outer carton just above the company names so as not to obscure any marking.

6.7.2 Re-Supply

Reorders should be emailed directly to BMS using [contact] and [contact] for shipment within 5 business days. When assessing need for resupply, institutions should keep in mind the number of vials used per treatment dose, and that shipments may take 5 business days from BMS receipt of request. Drug is not patient specific. Be sure to check with your pharmacy regarding existing investigational stock to assure optimal use of drug on hand.

6.8 Ipilimumab Accountability

It is the responsibility of the investigator to ensure that a current record of ipilimumab disposition is maintained at each study site where ipilimumab is inventoried and disposed. Records or logs must comply with applicable regulations and guidelines, and should include:

- Amount received and placed in storage area.
- Amount currently in storage area.
- Label ID number or batch number and use date or expiry date.
- Dates and initials of person responsible for each ipilimumab inventory entry/movement.
- Amount dispensed to and returned by each subject, including unique subject identifiers.
- Amount transferred to another area/site for dispensing or storage.
- Non-study disposition (e.g., lost, wasted, broken).
- Amount destroyed at study site.

6.9 **Ipilimumab Destruction**

If ipilimumab is to be destroyed on site, it is the investigator's responsibility to ensure that arrangements have been made for disposal and that procedures for proper disposal have been established according to applicable regulations, guidelines, and institutional procedures. Appropriate records of the disposal must be maintained.

7 ADVERSE EVENT REPORTING

7.1 Collection of Safety Information

The OHSU IRB defines an Unanticipated Problem (UP) as an event that is not expected given the nature of the research procedures and the patient population being studied and suggests that the research places patients or others at a greater risk of harm or discomfort related to the research than was previously known or recognized. Harm to a patient need not occur for an event to be a UP.

Reportable Adverse Event – AEs which qualify as unanticipated problems that must be reported by the PI to the IRB and by the IRB to the Institutional Official and to OHRP are categorized as follows:

- On Protocol Serious Adverse Events (SAEs) that are unexpected and related or possibly related to participation in the research.
- On Protocol SAEs or AEs that are expected in some patients, are related or possibly related, but are determined to be occurring at a significantly higher frequency or severity than expected.
- On or Off Protocol Unexpected SAEs or AEs that are related or possibly related, regardless of severity, that may alter the IRB's analysis of the risk versus potential benefit of the research and, as a result, warrant consideration of substantive changes in the research protocol or informed consent process/document.

Other events that are On or Off Protocol and unexpected that may place patients or others at a greater risk of harm or discomfort than was previously known or recognized. Harm to a patient need not have occurred.

All Reportable Adverse Events, as defined in this section occurring after patient enrollment must be reported to the Principal Investigator, [name] at [contact], [name], or [contact]. The Principal Investigator has the obligation to report all serious adverse experiences to the FDA, OHSU IRB, Bristol-Myers Squibb, and other participating sites in accordance with the following guidelines.

7.1.1 Serious Adverse Events

A serious adverse event (SAE) is any untoward medical occurrence that at any dose:

- results in death
- is life-threatening (defined as an event in which the subject was at risk of death at the time of the event; it does not refer to an event that hypothetically might have caused death if it were more severe)
- requires inpatient hospitalization or causes prolongation of existing hospitalization (see "note" below for exceptions)
- results in persistent or significant disability/incapacity
- is a congenital anomaly/birth defect
- is an important medical event (defined as a medical event(s) that may not be immediately life-threatening or result in death or hospitalization but, based upon appropriate medical and scientific judgment, may jeopardize the subject or may require intervention [eg, medical, surgical] to prevent one of the other serious

outcomes listed in the definition above.) Examples of such events include, but are not limited to, intensive treatment in an emergency room or at home for allergic bronchospasm; blood dyscrasias or convulsions that do not result in hospitalization.)

• Although overdose and cancer are not always serious by regulatory definition, these events should be reported on an SAE form and sent to BMS in an expedited manner. An overdose is defined as the accidental or intentional ingestion or infusion of any dose of a product that is considered both excessive and medically important.

NOTE: The following hospitalizations are not considered SAEs in BMS clinical studies:

- a visit to the emergency room or other hospital department for less than 24 hours that does not result in admission (unless considered an "important medical event" or a life-threatening event)
- elective surgery, planned before signing consent
- admissions as per protocol for a planned medical/surgical procedure
- routine health assessment requiring admission for baseline/trending of health status (eg, routine colonoscopy)
- medical/surgical admission for purpose other than remedying ill health state and was planned prior to entry into the study. Appropriate documentation is required in these cases
- admission encountered for another life circumstance that carries no bearing on health status and requires no medical/surgical intervention (eg, lack of housing, economic inadequacy, care-giver respite, family circumstances, administrative).

Note that all pregnancies, regardless of outcome, must be reported to the sponsor on a Pregnancy Surveillance Form, not an SAE form. All pregnancies must be reported and followed to outcome, including pregnancies that occur in the female partner of a male study subject.

7.1.2 Nonserious Adverse Events

All adverse events that are not classified as serious.

7.2 Assignment of Adverse Event Intensity and Relationship to Investigational Product

All adverse events, including those that are serious, will be graded according to the National Cancer Institute Common Toxicity Criteria for Adverse Events (NCI CTCAE), Version 4.0.

The following categories and definitions of causal relationship to investigational product as determined by a physician should be used for adverse events:

- Certain: There is a reasonable causal relationship between the investigational product and the AE. The event responds to withdrawal of investigational product (dechallenge), and recurs with rechallenge when clinically feasible.
- Probable: There is a reasonable causal relationship between the investigational product and the AE. The event responds to dechallenge. Rechallenge is not required.
- Possible: There is reasonable causal relationship between the investigational product and the AE. Dechallenge information is lacking or unclear.
- Not likely: There is a temporal relationship to investigational product administration, but there is not a reasonable causal relationship between the investigational product and the AE.
- Not Related: There is not a temporal relationship to investigational product administration (too early, or late, or investigational product not taken), or there is a reasonable causal relationship between noninvestigational product, concurrent disease, or circumstance and the AE.

The expression "reasonable causal relationship" is meant to convey in general that there are facts (eg, evidence such as de-challenge/re-challenge) or other arguments to suggest a positive causal relationship.

7.3 Collection and Reporting

Adverse events can be spontaneously reported or elicited during open-ended questioning, examination, or evaluation of a subject. (In order to prevent reporting bias, subjects should not be questioned regarding the specific occurrence of one or more AEs.)

If known, the diagnosis of the underlying illness or disorder should be recorded, rather than its individual symptoms. The following information should be captured for all AEs: onset, duration, intensity, seriousness, relationship to investigational product, action taken, and treatment required. If treatment for the AE was administered, it should be recorded in the medical record.

The investigator shall supply the sponsor and Ethics Committee with any additional requested information, notably for reported deaths of subjects.

7.3.1 Serious Adverse Events

Following the subject's written consent to participate in the study, all SAEs must be collected, including those thought to be associated with protocol-specified procedures. All SAEs must be collected that occur within 70 days of discontinuation of dosing of the investigational product. If applicable, SAEs must be collected that relate to any later protocol-specified procedure (eg, a follow-up skin biopsy). The investigator should notify

BMS of any SAE occurring after this time period that is believed to be certainly,

probably, or possibly related to the investigational product or protocol-specified

procedure.

All SAEs whether related or unrelated to the ipilimumab, must be immediately reported

to BMS (by the investigator or designee) within 24 hours of becoming aware of the event.

If only limited information is initially available, follow-up reports are required. The

original SAE form must be kept on file at the study site.

Participating centers will notify the Lead Site, OHSU, of all SAEs within 24 hours of

becoming aware of the event. Reporting will occur by MedWatch Form 3500A with

supporting documentation. OHSU will report this information to BMS and/or the FDA,

as appropriate.

All SAEs should be faxed or emailed to BMS at:

Global Pharmacovigilance & Epidemiology

Bristol-Myers Squibb Company

[contact]

Email: [contact]

For studies conducted under an Investigator IND, any event that is both serious and

unexpected must be reported to the FDA as soon as possible and, in no event, later than 7

days (death or life-threatening event) or 15 days (all other SAEs) after the investigator's

or institution's initial receipt of the information. BMS will be provided with a

simultaneous copy of all adverse events filed with the FDA. SAEs should be reported on

the MedWatch Form 3500A, which can be accessed at:

http://www.accessdata.fda.gov/scripts/medwatch/.

MedWatch SAE forms should be sent to the FDA at:

MEDWATCH

[name]

[name]

Fax: [name] ([name])

http://www.accessdata.fda.gov/scripts/medwatch/

All SAEs should simultaneously be faxed or e-mailed to BMS at:

Ipilimumab IST Protocol Shell, Version 7: 17 March 2009

54

Global Pharmacovigilance & Epidemiology Bristol-Myers Squibb Company

[contact]

Email: [contact]

Serious adverse events, whether related or unrelated to investigational product, must be recorded on the SAE page and reported expeditiously to BMS (or designee) to comply with regulatory requirements. An SAE report should be completed for any event where doubt exists regarding its status of seriousness.

All SAEs must be immediately reported by confirmed facsimile transmission (fax) and mailing of the completed SAE page. In some instances where a facsimile machine is not available, overnight express mail may be used. If only limited information is initially available, follow-up reports are required. (Note: Follow-up SAE reports should include the same investigator term(s) initially reported.) In selected circumstances, the protocol may specify conditions that require additional telephone reporting.

If the investigator believes that an SAE is not related to the investigational product, but is potentially related to the conditions of the study (such as withdrawal of previous therapy, or a complication of a study procedure), the relationship should be specified in the narrative section of the SAE page.

If an ongoing SAE changes in its intensity or relationship to the investigational product, a follow-up SAE report should be sent immediately to the sponsor. As follow-up information becomes available it should be sent immediately using the same procedure used for transmitting the initial SAE report. All SAEs should be followed to resolution or stabilization.

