For weeks 12-24, patients are observed for progression.

Patients who do not progress by week 24 will receive ipilimumab 10 mg/kg IV every three months for weeks 24-60.

Patients will be followed for 5 years after completion of study treatment

PROTOCOL SYNOPSIS

Protocol Title:	A Phase II Study of CTLA Blockade by Ipilimumab plus Androgen Suppression Therapy in Patients with an Incomplete Response to AST Alone for Metastatic Prostate Cancer			
Site Numbers & Names:	This study is currently open at Oregon Health & Science University and Rutgers Cancer Institute of New Jersey.			
Research Hypothesis:	The early addition of immunotherapy in patients with metastatic prostate cancer who have a poor prognosis as a result of an incomplete biochemical response to androgen suppression therapy (AST) will improve outcomes to approximate outcomes in patients who do obtain a complete biochemical response with AST.			
Study Schema: Drugs / Doses / Length of Treatment)	All patients will receive ipilimumab 10 mg/kg by 90-minute IV infusion every three weeks for four doses. Patients without progression at Week 24 will subsequently receive maintenance ipilimumab 10 mg/kg IV every 12 weeks for four additional doses. Patients will have their PSA checked every three weeks during the first four doses of ipilimumab, every six weeks between weeks 12 and 24, and every 12 weeks thereafter. Once all eight doses of ipilimumab have been given, patients will be followed with a serum PSA every 12 weeks (either at the research site or at the patient's treating physician) until radiographic progression. Survival status will be assessed by telephone every 6 months for as long as patients are alive for up to 5 years after their last study visit. There will be a CT scan of the chest/abdomen/pelvis and whole body bone scans at baseline, 12 weeks, 24 weeks, and then every three months until radiographic progression. Scans may be performed sooner if there are any concerns about progression. Correlative study labs will be drawn just prior to ipilimumab administration during the first four doses (weeks 1, 4, 7, 10).			

Study Objectives:	The primary endpoint is the proportion of patients who achieve an undetectable PSA (≤ 0.2 ng/ml) after initiation of ipilimumab therapy.

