Patients with a life expectancy less than 6 months, treatment with any investigational agent in the last 28 days, more than 18 months since initiation of AST, or a concurrent active malignancy diagnosed within the last 5 years (other than non-melanoma skin cancer, or other readily treatable tumors with expected cure) will not be eligible for this study. Patients must not have a known autoimmune disease, use prednisone > 10 mg daily (or its equivalent) orally for any indication, or have chronic infections (including hepatitis B or C or HIV).

Criteria for Evaluation: (Efficacy, safety, stopping rules, etc.)

Patients will receive a history and physical exam and multiple laboratory tests (PSA, complete chemistry panel and blood counts, as well as tests for endocrinopathies) at baseline and every 3 weeks during the first 4 doses of therapy. Available labs (i.e. the chemistry panel and blood counts) will be reviewed prior to administration of ipilimumab. Imaging studies will be done at baseline, 12 weeks, 24 weeks and then every six months, or sooner if concerning symptoms arise. If there is no evidence of radiographic progression on the 24-week scan, patients will go on to receive four doses of maintenance ipilimumab therapy (weeks 24, 36, 48, 60). They will have a history and physical exam at least every three months. Their survival status will be assessed by phone survey every 6 months for up to five years after the last study visit.

Efficacy will be based on the results of the PSA and imaging studies (using PCWG2 and modified RECIST criteria). Safety will be monitored using the regular physician examinations and laboratory assessments.

Statistics:

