3.6 Follow-up visits after completion of ipilimumab therapy

Patients will be followed with a history, physical exam, CT and NM bone scan and serum PSA quarterly along with treatment visits during the maintenance treatment phase, until radiographic progression. If a patient has not met radiographic progression by Week 60 visit, the patient will be followed by PSA and scans until radiographic progression. Following radiographic progression, patients will be followed by semi-annual phone surveys with the patient, his family, or his treating physician to collect data on treatment status and overall survival for up to 5 years after all protocol treatment has been completed.

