6 STUDY PROCEDURES AND OBSERVATIONS

6.1 Time and Events Schedule for Protocol CA184059

		Induction* (Cycles 1-4)			Between Treatments			Maintenance* (Cycles 5-8)			Every 6 Month Follow Up*		
T //P 1	Scree . #	Wk	Wk	Wk	Wk	Wk	Wk	Wk	11/1 24	WI 26	XX/1 40	W/I (0	Evel Fc
Test / Procedure	ning#	1	4	/	10	12	18	23/24	Wk 24	Wk 36	Wk 48	Wk 60	Π
Informed Consent	X												
Inclusion / Exclusion Criteria	X												
Demographics, medical history, concurrent medical conditions	X												
Testosterone level	X												
Serum samples for hepatitis panel and HIV, if high index of suspicion	X												
ECOG performance status	X	X	X	X	X	X	X	X	X	X	X	X	
Blood collection for correlative studies ¹		X	X	X	X								
Physical Exam	X	X	X	X	X	X	X	X	X	X	X	X	
Vital Signs	X	X	X	X	X	X	X	X	X	X	X	X	
Weight		X	X	X	X				X	X	X	X	
Bone Scan ²	X					X		X		X	X	X	
Chest, Abdomen & Pelvis CT ²	X					X		X		X	X	X	

CBC with differential	X	X	X	X	X	X	X	X	X	X	X	X	
Chemistry Panel: Creatinine, BUN, electrolytes (sodium, potassium, chloride), glucose, bilirubin alkaline phosphatase, ALT, AST, calcium, ³	X	X	X	X	X	X	X	Х	Х	X	Х	X	
LDH	X												
Autoimmune Profile: TSH, free T4	X	X	X	X	X				X	X	X	X	
PSA ⁴	X	X	X	X	X	X	X	X	X	X	X	X	
Concurrent medications (include documentation of androgen suppression therapy)	X	X	X	X	X				X	X	X	X	
Adverse Effects Recorded	X	X	X	X	X		_		X	X	X	X	
Ipilimumab		X	X	X	X				X	X	X	X	
Telephone Contact													X

^{*} Cycle 1-8 procedures can be done +/- 3 days and Long Term Follow-Up can be done +/- 2 weeks.

#Screening procedures must be done within 28 days of first treatment

^{**}PSA, Autoimmune profile, LDH, CBC Diff, Chem panel including Creatinine, BUN, electrolytes (sodium, potassium, chloride), glucose, bilirubin, alkaline phosphatase, ALT, AST, calcium, phosphorus and Correlative **baseline samples** DO NOT need to be repeated on Cycle 1 Day 1 if done within 7 Days of Cycle 1 Day 1

¹ Per outlined correlative studies

² Imaging Studies will also be done every three months until radiographic progression

³ Available labs (i.e. chemistries and blood counts) will be reviewed prior to each infusion

⁴ PSA will be done until radiographic progression

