6.3.2 Safety Assessments

All patients who receive at least one dose of ipilimumab will be considered evaluable for safety parameters. Additionally, any occurrence of a SAE from time of consent forward, up to and including follow-up visits will be reported. See Section 8: Adverse Event Reporting.

Safety will be evaluated for all treated patients using the National Cancer Institute (NCI) Common Terminology Criteria for Adverse Events (CTCAE), Version 4.0 (http://ctep.cancer.gov). Safety assessments will be based on medical review of adverse event reports and the results of vital sign measurements, physical examinations, and clinical laboratory tests.

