6.4 Criteria for Evaluation

6.4.1 Safety Evaluation

Refer to the NCI CTCAE, Version 4.0 (http://ctep.cancer.gov). SAEs will be assessed every three weeks during the first four cycles of ipilimumab and every 12 weeks during the fifth through eighth cycle of ipilimumab.

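### The SAE collection window is stated two ways, and no contact after dose 8, or between dose 4 and week 24, is marked for adverse-event recording

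*Combined protocol and SAP*

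**What the plan says.** Two sections set the period for serious adverse events.

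- Section 6.3.2 (Safety Assessments): "any occurrence of a SAE from time of consent forward, up to and including follow-up visits will be reported". It gives no day limit, and refers the reader to the adverse-event section.
- Section 7.3.1 (Serious Adverse Events): "All SAEs must be collected that occur within 70 days of discontinuation of dosing of the investigational product". After that the investigator should notify "BMS of any SAE occurring after this time period that is believed to be certainly", probably or possibly related to the drug or to a protocol procedure.

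Section 7.3.3 starts collection of nonserious events at the first dose and requires follow-up of ongoing ones. It gives no last day for new ones.

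On scheduled enquiry, section 6.4.1 has SAEs assessed every three weeks in the first four cycles and "every 12 weeks during the fifth through eighth cycle of ipilimumab". In the Time and Events Schedule (6.1), the row "Adverse Effects Recorded" is marked at screening and at weeks 1, 4, 7, 10, 24, 36, 48 and 60. It is not marked at weeks 12, 18 or 23/24. The long-term follow-up column carries only a telephone contact.

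After week 60, section 3.6 names PSA and scans until radiographic progression, then six-monthly calls "to collect data on treatment status and overall survival for up to 5 years after all protocol treatment has been completed". The synopsis and section 6.4.2 let the PSA be drawn by an outside physician. Section 6.2.1 is headed for study completion as well as early discontinuation, but its text documents adverse events only at early withdrawal.

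IRAEs and their correlation with outcome are secondary objectives (2.2), to be analysed by logistic and Cox regression (8.5). No ascertainment window is given for them.

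**The concern.** A site that follows 6.3.2 and a site that follows 7.3.1 can both comply and still return different SAE counts. The safety tabulation in 8.6 sets no window that would settle the matter.

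The schedule also leaves gaps where delayed immune toxicity could occur. The last marked recording falls on the day of dose 8, so it covers dose 7 and earlier but nothing caused by dose 8. The same happens after dose 4, where three visits take place with examination, vital signs and laboratory tests but without an adverse-event mark.

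Two things are at stake. One is the completeness of the safety record after the last dose of each phase. The other is whether the IRAE variable used in 8.5 is measured with similar opportunity in men who stay on treatment and men who do not.

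**Working it through.** The plan gives no figure on this point to reproduce. The check sets the sections side by side and counts weeks.

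**1. Where the two windows differ**

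| Event | 6.3.2 | 7.3.1 |
|---|---|---|
| Any SAE from consent to day 70 after dosing stops | reported | collected |
| SAE after day 70, judged at least possibly related to drug or procedure | reported while follow-up visits last | notified, no end date |
| SAE after day 70, judged unrelated | reported while follow-up visits last | not required |

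The practical difference is the last row.

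**2. After dose 8**

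Inputs: dose 8 at week 60 (synopsis and 6.1); 70-day window (7.3.1); scans and PSA every three months (3.6, 6.1 footnotes).

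- Window closes: 60 + 70/7 = week 70.
- Next quarterly scan or PSA: about week 72, which is (72 − 60) × 7 = 84 days after dose 8 and 84 − 70 = 14 days after the window closes. If the two-week tolerance for long-term follow-up applies to it, it falls between day 70 and day 98.
- First six-monthly call, assuming it is timed from dose 8: about day 183, some 113 days after the window closes.

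At nominal timing no scheduled contact falls inside weeks 60 to 70. Neither later contact is marked for adverse events.

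**3. After dose 4**

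- Dose 4 is at week 10. The next marked recording is week 24: (24 − 10) × 7 = 98 days.
- The visits at weeks 12, 18 and 23/24 lie in between without a mark.
- The week-24 mark stands in the maintenance block, so it serves men who go on to dose 5.

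**4. Drug exposure, for context only**

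Section 1.3.3 gives a half-life of 297 to 414 h. Seventy days is 1,680 h.

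- 1,680/414 = 4.1 half-lives, leaving 0.5^4.06 = 6.0%.
- 1,680/297 = 5.7 half-lives, leaving 0.5^5.66 = 2.0%.

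Drug from dose 8 is therefore present through much of the unmarked period. This assumes simple exponential decline and counts no events.

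**5. Opportunity to record an IRAE**

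- Completer: weeks 1, 4, 7, 10, 24, 36, 48, 60 = 8 marked on-treatment recordings.
- Man who stops after induction: weeks 1, 4, 7, 10 = 4, plus any record made at withdrawal under 6.2.1.

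**The case against.** The other side has real points.

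- Section 6.3.2 points straight to the adverse-event section (as section 8, its number in the table of contents; it is now section 7). One can argue that 7.3.1 is meant to govern. The pointer does not say that it overrides the sentence before it, so the wording still needs reconciling, but the conflict is narrow.
- A reader might infer that toxicity from the last dose is simply not sought. The documents do not support that. Section 7.3.1 makes SAE collection to day 70 mandatory and keeps related SAEs notifiable afterwards. Section 7.3 allows events to be elicited by open questioning or examination. What is missing is a scheduled contact at which this is marked to happen.
- The synopsis promises a history and examination at least every three months with no end date, and a 12-week eighth cycle in 6.4.1 could be read to reach week 72. Section 3.6, however, ties the history and examination to the maintenance visits, and 6.1 shows no such visit after week 60. The data and safety monitoring plan is a separate document that could add checks; it cannot be judged here.
- A reader might also infer that the 70-day rule itself biases the IRAE correlation, because the window would close at week 20 for a man whose last dose was at week 10 and at week 70 for a completer. That does not follow. Serious IRAEs are drug-related by definition and stay notifiable after day 70. The 70-day rule does not cover nonserious events. A man withdrawn for progression has events documented under 6.2.1. The dating is also uncertain, because 7.3.1 does not say whether discontinuation means the last dose or the decision to stop.
- The 26% rate of drug-related SAEs at 10 mg/kg (1.3.4.2) might be taken as the size of the gap. It is an overall rate, not a rate after an eighth dose, and section 1.4 places IRAEs typically in induction. It sizes nothing here.

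The inconsistency between the two windows, the unmarked intervals and the unequal number of recordings remain.

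**Conclusion.** The point holds in limited form and is worth acting on because correction is cheap.

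- The two SAE windows disagree, in effect for unrelated SAEs after day 70.
- No contact is marked for adverse-event recording in the 70 days after dose 8, or in the 98 days between dose 4 and week 24. Recording there relies on spontaneous report or on what an examination happens to show.
- Marked recordings number eight for completers and four, plus any withdrawal record, for men who stop after induction. This can favour finding IRAEs in men who do well, chiefly nonserious IRAEs, since serious related events are notifiable throughout.

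The number of events that would be missed cannot be estimated: the documents give neither an event rate after dose 8 nor the number of men expected to reach it. The reading assumes that 6.1 is the operative schedule and that visits occur at nominal times. The primary PSA endpoint and the two-stage design are unaffected.

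**What to change.** 1. Reconcile 6.3.2, 7.3.1 and 7.3.3 to one stated collection window, with a start and an end for serious and for nonserious events. The choice is the sponsor's. Say whether discontinuation of dosing is dated from the last dose given or from the decision to stop.
2. In 6.1, mark adverse-event review at the existing week 12, 18 and 23/24 visits.
3. Add one adverse-event review at or after 70 days from the last dose for every man, whatever the reason for stopping. It can be a telephone call or, for completers, the scan visit due at about week 72. For a man whose last dose was at week 10, the week 23/24 visit already qualifies, at (23 − 10) × 7 = 91 days or later.
4. In 8.5, count IRAEs for the outcome correlation over the same window in all men, for example to week 24. With item 2 in place, men followed that long have 4 + 3 = 7 common recordings by week 23/24.

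Cost: protocol wording, marks at visits already planned, and about 30 brief contacts for 30 patients. Expect a slightly higher event count. If the 70-day window is chosen, unrelated late SAEs that 6.3.2 would have collected are lost, and the protocol should say that this is intended.
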